5.2.2. Analyses for Continuous Data

Descriptive statistics n, mean, median, standard deviation, minimum, and maximum will be used to summarize the endpoints. The differences of each PF-06649751 treatment versus the placebo group with 90% confidence intervals from the fitted model will be reported.

5.2.2.1. Mixed Model for Repeated Measures Analysis (Non-Bayesian Approach)

The Mixed Model for Repeated Measures (MMRM) analysis will be based on an analysis of a restricted maximum likelihood (REML)-based mixed model. The response variable will be the change from baseline to each post baseline visit, and the model will include the following fixed effects:

- randomized treatment (with 5 levels: PF-06649751 1 mg QD, 3 mg QD, 7 mg QD, 15 mg QD, and placebo), a categorical factor;
- visit, a categorical factor;
- treatment-by-visit interaction;
- baseline endpoint value, a continuous covariate;
- baseline-by-visit interaction;
- geographic region as appropriate (e.g. North America, Japan, and Europe).

In addition, cohort (Part A, Part B) may also be included as a fixed effect as appropriate.

An unstructured variance-covariance structure will be used to model the within-subject errors. In the unlikely event that the computational algorithm fails to converge, the following structures will be executed in the order specified (essentially in decreasing order of complexity) until convergence is achieved: heterogeneous Toeplitz, heterogeneous first-order

autoregressive, autoregressive, heterogeneous compound symmetry, compound symmetry, and variance components. The first structure yielding convergence will be used as the primary analysis. The Kenward and Roger method⁷ will be used for calculating the denominator degrees of freedom for tests of fixed effects. OM option will be used to derive the least squares means similar to the observed margins. Example SAS code for the MMRM model will be provided in the Programmer's Analysis & Reporting documentation.

The least-squares mean estimates, standard errors, and two-sided 90% CIs for each treatment groups will be reported. The efficacy comparisons based on the treatment difference vs. placebo estimated using least-squares means for each PF-06649751 dose will be conducted, and their point estimates, standard errors, and two-sided 90% CIs will be reported.

The assumptions of normality will be verified graphically using residual plots. For each fitted model, studentized residual plots will be produced. The residual plots will not be included in the clinical study report, but will be sent to the statistician for inspection at the time the analysis is conducted.

5.2.2.2. Dose Response Analysis (Non-Bayesian Approach)

A four parameter E_{\max} model will be used to estimate the dose response relationship. The model is as follows:

$$y = E_0 + \frac{E_{\max} \cdot D^\lambda}{ED_{50}^\lambda + D^\lambda}; \text{ where,}$$

- y is the endpoint change from baseline;
- D is the PF-06649751 dose in mg;
- E_0 is the placebo response;
- E_{\max} is the additive increase over placebo in the response of PF-06649751 at a theoretically infinite dose;
- ED_{50} is the PF-06649751 dose in mg that provides an effect of $E_0 + E_{\max}/2$;
- λ is the Hill parameter and measures the steepness of the dose response curve.

The non-linear dose response model will be fitted in two stages: a MMRM model described in [Section 5.2.2.1](#) will firstly be modelled to the repeated measures data, and the response least squares estimates for the specified visit time as well as the estimated covariance matrix for the response estimates will be obtained. These MMRM estimates will then be fitted to the E_{\max} model, based on the generalized least squares criterion using the inverse of the covariance matrix S as the weighting matrix: $(f(dose, \theta) - resp)' S^{-1} (f(dose, \theta) - resp)$. This fitting is based on the asymptotic normality assumption of the first stage MMRM estimates.

Example R code for the dose response model utilizing DoseFinding package will be provided in the Programmer's Analysis & Reporting documentation.

The efficacy comparisons will be based on the treatment difference vs. placebo estimated from this E_{\max} model fit. Their point estimates and two-sided 90% CIs from the fitted model will be reported.

An acceptable range of a true effect for an minimum effective dose (MED) will be evaluated from the E_{\max} model, and is defined as the lowest PF-06649751 efficacious dose that

- is within the range of tested doses in the study,
- has a lower tested dose that is not efficacious, and
- has a placebo-corrected point estimate between 1.5 and 2 hours.

5.2.2.3. Bayesian Analysis

In Bayesian analysis approach, Bayesian methods will be used to estimate the posterior distribution of the treatment effect. This will be done by combining the data from the study with prior belief about the placebo response.

Informative priors for the placebo response were derived from a Bayesian predictive meta-analysis of a few recent and diverse Parkinson's disease studies. It is possible that whilst the study is ongoing, data information from more sources may become available for incorporation into the informative prior for the placebo effect. The priors specified in this SAP may therefore be amended prior to final study reporting. Any change to the SAP-specified priors will be documented in the CSR.

The informative priors for the placebo effect are defined as

- Prior for the placebo effect for daily OFF time change from baseline $\sim N(-1.0, 0.602)$

A robust mixture prior approach (Bolstad 2007)² will be used for all Bayesian analysis when incorporating informative prior for the placebo effect. The robust mixture informative prior takes into account that should the final data on the endpoint be sufficiently different to the prior perceived knowledge of placebo, then low-informative priors will be used rather than the informative priors. The informative prior is initially weighted with a 90% probability, with a 10% weight to the low-informative prior. The actual weighting of the informative and low-informative priors will be estimated from the data.

A low-informative prior is defined as a distribution with large variance, e.g. $N(0, 10^6)$.

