5.2.2.3.2. Bayesian Dose Response Model

In Bayesian dose response analysis, the same four parameter E_{\max} model as described in Section 5.2.2.2 will be used to model the dose response relationship. The least squares estimates and their covariance from MMRM analysis described in Section 5.2.2.1 will be inputted in the Bayesian analysis. Robust mixture informative prior will be used for the placebo effect, and weak empirically-based prior distributions, based on meta-analysis of many dose response studies (Thomas et al 2014), will be used for the other model parameters. These weak priors are defined in this study as:

- Prior for $E_{\max} \sim N(0, 10^6)$;
- Prior for $ED_{50} = \exp(ed50t) * \text{projected } ED_{50}$ (which is 3mg projected for PF-06649751 based on Ph1 studies), where $ed50t \sim t$ distribution $t(0.79, 2.78, 5)$;
- Prior for $\lambda = 6 * lamt$, where $lamt \sim dbeta(3.03, 18.15)$.

Example R and JAGS code for the Bayesian E_{\max} model will be provided in the Programmer's Analysis & Reporting documentation. The efficacy comparisons will be based on the treatment difference vs. placebo estimated from this Bayesian E_{\max} model. Their posterior point estimates and two-sided 90% credible intervals from the fitted model will be reported. MED will be similarly evaluated as described in [Section 5.2.2.2](#).

A Bayes posterior predictive test for the monotonicity of the Emax fit will be conducted by computing the probability that the maximum response from lower doses (all 3 lower doses in this case) compared to the response from the highest dose is no better than predicted by the model (eg, Thomas et al 2014). Example R function code will be provided in the Programmer's Analysis & Reporting documentation. A Bayes predictive probability of < 0.05 will reject the monotonic Emax fit.

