6.1.1.1. Primary Analysis

Endpoint: Daily OFF time

- Analysis time points: Week 10 (End of Period A)
- Analysis population (method of imputation for missing data): FAS (See Section 3.1)
- Analysis methodology

Change from baseline will primarily be analyzed using the Bayesian Dose Response Analysis (See Section 5.2.2.3.2). If the Bayes posterior predictive test rejects the monotonic Emax fit (prob < 0.05), then the primary analysis will be based on the MMRM analysis (See Section 5.2.2.1). An overall dose-response trend test (See Section 5.2.2.4) will also be performed to control family-wise error rate.

- Supporting objective and Decision rule: Primary Objective (See [Section 2.1.1](#)), Secondary Objective (See [Section 2.1.2](#)), and Decision rules C1, C2 (See [Section 5.1.2](#))

Reporting results:

- Raw data: The sample size, mean, standard deviation, median, minimum and maximum at baseline and post-baseline visits will be presented for each treatment arm.
- Change from baseline: The sample size, mean, standard deviation, median, minimum and maximum will be presented for each treatment arm. The Bayesian point estimates, 90% credible interval, difference from placebo for each pair of treatment groups and the corresponding 90% credible interval will be presented. The MED estimate if applicable will be presented.

Figures

- Vertical bar chart of Change from Baseline Bayesian point estimates and 90% credible interval at Week 10.
- Bayesian Emax model graph with the MMRM estimates.
- Change from baseline time profile per MMRM for each treatment group.

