6.1.1.2. Sensitivity/Robustness Analyses

To support the interpretation of the primary analysis the following analyses will be performed:

Endpoint: Daily OFF time

- Analysis time points: Week 10 (End of Period A);
- Analysis populations (method of imputation for missing data): FAS, PPAS, FAS-Cohort 1 only, FAS-Cohort 2 only (See [Section 3.1](#));
- Analysis methodology: Change from baseline will be analyzed using the MMRM analysis (See [Section 5.2.2.1](#); FAS, FAS-Cohort 1 only), Bayesian ANOVA analysis (See [Section 5.2.2.3.1](#); FAS, FAS-Cohort 1 only), Dose Response analysis (See [Section 5.2.2.2](#); FAS, FAS-Cohort 2 only), and Bayesian Dose Response analysis (See [Section 5.2.2.3.2](#); PPAS, FAS-Cohort 2 only).

Reporting results:

- Raw data: The missing data pattern will be shown by treatment group and overall, for the Hauser Diary up to Week 10.
- Change from baseline: The point estimate, 90% confidence or credible interval for the point estimate, difference from placebo for each pair of treatment groups and the corresponding 90% confidence or credible interval will be presented. The MED estimate if applicable will be presented.

Figures

- Empirical cumulative distribution function showing % of subjects with change from baseline \leq cutoff value at Week 10 by treatment group; (any drop outs are assigned to the left side of x axis).

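### If the SAP's example N(0, 10^6) is the component coded, the placebo-prior fallback is nearly inert: the informative prior keeps over 99% weight until placebo misses -1.0 h by about 2.8 h (2.4 h if 0.602 is an SD)

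*SAP*

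**What the plan says.** SAP 5.2.2.3 gives the placebo change in daily OFF time an informative prior, N(-1.0, 0.602), inside a robust mixture. Its stated purpose is that "should the final data on the endpoint be sufficiently different to the prior perceived knowledge of placebo, then low-informative priors will be used" in place of the informative ones. On the weights: "The informative prior is initially weighted with a 90% probability, with a 10% weight to the low-informative prior". The final weighting is to be estimated from the data. The other component is described only by example: "A low-informative prior is defined as a distribution with large variance, e.g. $N(0, 10^6". No threshold for conflict is given, and 0.602 is not labelled as a variance or an SD.

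The mixture enters the primary model in SAP 5.2.2.3.2: "Robust mixture informative prior will be used for the placebo effect, and weak empirically-based prior distributions" for the remaining parameters. That model supplies the estimates for C1, C2 and the 1.5-2 h MED band.

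The SAP's one explicit trigger for leaving this model is the monotonicity test: "A Bayes predictive probability of < 0.05 will reject the monotonic Emax fit". SAP 6.1.1.1 then makes MMRM primary. Protocol 9.2.1 is wider: MMRM becomes primary if the Emax model is considered unsuitable for the data.

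Fits without the placebo prior are planned in SAP 6.1.1.2 ("To support the interpretation of the primary analysis the following analyses will be performed"), and a primary figure is the "Bayesian Emax model graph with the MMRM estimates".

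**The concern.** A mixture weight is updated by how well each component predicted the observed placebo mean. A component with an SD of 1000 h spreads its density so thinly that it predicts every plausible mean badly. It therefore loses weight even when the informative component is clearly wrong. The fallback is written down but would seldom act.

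At stake are the primary dose-versus-placebo estimates. If placebo patients improve much more than 1.0 h, the model pulls the placebo estimate back towards -1.0 h and every active dose looks better than it is. If placebo patients worsen, an effective dose looks worse.

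**Working it through.** **Inputs.** Prior N(-1.0, 0.602), weights 90:10 and example N(0, 10^6) from SAP 5.2.2.3; SD 2.9 h and 32 evaluable per arm from Protocol 9.1. The SAP calls 10^6 a large variance, which favours reading 0.602 as a variance too. Both readings are shown.

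**The plan's own figures.** SE of a difference = 2.9 x sqrt(2/32) = 0.725 h. P(estimate >= 1.5) is 1 - Phi((1.5 - 2.25)/0.725) = 85% for a true effect of 2.25 h, and 1 - Phi(1.5/0.725) = 1.9% for no effect. These match Protocol 9.1 without using the placebo prior.

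**Weights, placebo arm alone.** Variance of the placebo mean = 2.9^2/32 = 0.263. The informative component predicts that mean with variance 0.602 + 0.263 = 0.865 (SD 0.930 h). For a miss of m hours from -1.0:

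odds (informative : low-informative) = 9 x (1000/0.930) x exp(-m^2/(2 x 0.865)) = 9678 x exp(-m^2/1.730)

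- 99% informative: m = sqrt(1.730 x ln(9678/99)) = 2.82 h.
- 50% informative: m = sqrt(1.730 x ln 9678) = 3.98 h.
- At m = 2 h the low-informative weight is 0.1%, down from the starting 10%.

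On the SD reading the predictive variance is 0.602^2 + 0.263 = 0.625. The same steps give 2.44 h, 3.42 h and 0.2%. If 0.602 were a precision, the 99% point would be 4.0 h. In the full Emax model the active arms move the 99% point to about 2.5-3.0 h (variance) or 2.1-2.5 h (SD).

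**Pull.** While the informative weight is near 1, the placebo mean is shrunk by 0.263/0.865 = 30% of the miss (42% as SD). That is 0.6 h (0.84 h) at a 2 h miss in a two-arm comparison, against a 1.5 h criterion. The prior is worth 2.9^2/0.602 = 14 placebo patients (23 as SD).

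**Unit-information component N(-1.0, 2.9^2), same 90:10 weights.** The 50% point moves to 2.54 h (2.18 h as SD). At a 2 h miss the low-informative weight is 22% (37%).

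**Primary Emax model, simulated.** Assumed true effects are 0.5/1.2/1.8/2.25 h at 1/3/7/15 mg. Settings: planned allocation less 10% (32.4 per arm, 48.6 on 15 mg), SD 2.9 h, priors of SAP 5.2.2.3.2, trend test applied, 10,000 trials per scenario, Monte Carlo error about 0.5 points. Ranges span two readings of 2.78 in the ED50 prior (scale, precision). Entries are the percentage passing C1 and C2 at a 2 h miss.

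| Scenario | Reading of 0.602 | N(0, 10^6) | N(-1.0, 2.9^2) | No borrowing |
|---|---|---|---|---|
| 3 mg (true 1.2 h), placebo -3.0 h | variance | 40-66 | 28-54 | 9-23 |
| | SD | 61-85 | 31-56 | 9-23 |
| 15 mg (true 2.25 h), placebo +1.0 h | variance | 59-71 | 64-77 | 82-91 |
| | SD | 46-56 | 59-74 | 82-91 |

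**Share due to the component**, pairing like ends of the ranges:

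- Variance reading, 3 mg: 40 - 28 = 12 and 66 - 54 = 12 points, of total excesses 40 - 9 = 31 and 66 - 23 = 43.
- Variance reading, 15 mg: 5 and 6 points, of shortfalls of 23 and 20.
- SD reading, 3 mg: 30 and 29 points, of 52 and 62.
- SD reading, 15 mg: 13 and 18 points, of 36 and 35.

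**Monotonicity switch.** The test compares the three lower active doses with 15 mg; placebo is not in the comparison. With the stated component (SD reading; 2,500 trials, Monte Carlo error about 0.4 points), rejection is 3.2-4.8% with no conflict, 3.7-3.9% at placebo -3.0 h and 1.9-2.4% at +1.0 h. With the switch included, 3 mg at -3.0 h still passes 56-82% and 15 mg at +1.0 h passes 44-55%.

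**Rarity under the informative prior.** An observed placebo mean 2 h or more from -1.0: 2 x P(Z > 2/0.930) = 3.2% (1.1% as SD). A true mean that far out: 2 x P(Z > 2/sqrt(0.602)) = 1.0% (0.09%).

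**The case against.** Several points on the other side have weight.

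- **The component is only an example.** The code sits in programming documentation that is not part of these documents. This stands, and the finding is conditional on it.
- **The SAP sets no threshold for conflict.** The 99% points lie about three predictive SDs out, so "too late" is an opinion about design. This partly stands. But at a 2 h miss, more than two predictive SDs out, the low-informative weight has fallen well below its starting 10%, which runs against the stated purpose.
- **Detection is planned.** The MMRM and non-Bayesian Emax fits, and the overlay of MMRM estimates, would show a conflict. This stands. They do not replace the primary estimate unless the Emax model is rejected or, under Protocol 9.2.1, considered unsuitable. The monotonicity test was not designed to find placebo conflict, so its silence is not a fault of that test.
- **The 10% weight** belongs to a diffuse component. It is not a stated 10% chance of a 2 h miss.

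A reader might infer that the component causes the whole distortion. It does not: on the variance reading most comes from the declared 90% informative weight, which is an open design choice. At a 1 h miss (SD reading) the two components give almost the same results: 26-50% against 23-47% for 3 mg. A reader might also infer inflated type I error. That is not shown: SAP 5.1.1 places a one-sided 0.05 trend test in front, and SAP 5.2.2.4 describes that test without the placebo prior.

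**Conclusion.** The concern holds in a limited form. If N(0, 10^6) is coded, the fallback in SAP 5.2.2.3 is nearly inert for any placebo miss below about 2.8 h (2.4 h if 0.602 is an SD), and no automatic rule in the SAP corrects the primary estimate for such a conflict.

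On the better-supported variance reading, the component itself accounts at a 2 h miss for about 12 of 31-43 excess points in the 3 mg pass rate, and 5-6 of 20-23 lost points at 15 mg. Its share is larger on the SD reading. The rest is declared borrowing. The case is rare under the prior, but it is the case the fallback exists for.

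The weights rest on 32 evaluable placebo patients and an SD of 2.9 h. The pass rates also rest on the assumed true effects and on independent arm means. It is worth fixing because the repair is cheap, not because the primary analysis is likely to fail.

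**What to change.** In SAP 5.2.2.3, replace N(0, 10^6) as the placebo mixture component with a unit-information component such as N(-1.0, 2.9^2), and state whether 0.602 is a variance or an SD.

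Report a short simulation of the primary Emax model under placebo conflict, with a no-borrowing fit as comparator, and use it to confirm the 90:10 starting weights. Say openly that the change is a partial remedy: the tabulated pass rates stay well away from the no-borrowing figures.

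The cost is a sentence or two in the SAP, the simulation, and at most about 0.5 points of 15 mg pass rate when the prior is right (on the SD reading, 89.7% to 89.4% or 95.1% to 95.0%).

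Separately, SAP 5.2.2.3 lets the priors be changed up to final reporting, provided the study report records it. Any amended placebo prior should be fixed before unblinding for the analysis that uses it, and priors set later should serve only as sensitivity analyses.

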5.2.2.3.1. Bayesian ANOVA Model

In Bayesian ANOVA analysis, treatment will be modelled as a fixed effect, and the least squares estimates and their covariance from MMRM analysis described in Section 5.2.2.1 will be input to the Bayesian analysis. Robust mixture informative prior will be used for the placebo effect, and low-informative prior will be used for all PF-06649751 dose effects. Example R and JAGS code for the Bayesian ANOVA model will be provided in the Programmer's Analysis & Reporting documentation.

The efficacy comparisons will be based on the treatment difference vs. placebo estimated from this Bayesian analysis. Their posterior point estimates and two-sided 90% credible intervals from the fitted model will be reported.

5.2.2.3.2. Bayesian Dose Response Model

In Bayesian dose response analysis, the same four parameter E_{\max} model as described in Section 5.2.2.2 will be used to model the dose response relationship. The least squares estimates and their covariance from MMRM analysis described in Section 5.2.2.1 will be inputted in the Bayesian analysis. Robust mixture informative prior will be used for the placebo effect, and weak empirically-based prior distributions, based on meta-analysis of many dose response studies (Thomas et al 2014), will be used for the other model parameters. These weak priors are defined in this study as:

- Prior for $E_{\max} \sim N(0, 10^6)$;
- Prior for $ED_{50} = \exp(ed50t) * \text{projected } ED_{50}$ (which is 3mg projected for PF-06649751 based on Ph1 studies), where $ed50t \sim t$ distribution $t(0.79, 2.78, 5)$;
- Prior for $\lambda = 6 * lamt$, where $lamt \sim dbeta(3.03, 18.15)$.

Example R and JAGS code for the Bayesian E_{\max} model will be provided in the Programmer's Analysis & Reporting documentation. The efficacy comparisons will be based on the treatment difference vs. placebo estimated from this Bayesian E_{\max} model. Their posterior point estimates and two-sided 90% credible intervals from the fitted model will be reported. MED will be similarly evaluated as described in [Section 5.2.2.2](#).

A Bayes posterior predictive test for the monotonicity of the Emax fit will be conducted by computing the probability that the maximum response from lower doses (all 3 lower doses in this case) compared to the response from the highest dose is no better than predicted by the model (eg, Thomas et al 2014). Example R function code will be provided in the Programmer's Analysis & Reporting documentation. A Bayes predictive probability of < 0.05 will reject the monotonic Emax fit.

5.2.2.4. Dose Response Trend Test

A test of the hypothesis of no effect for all doses will be performed at the one-sided 0.05 level. The MCP-MOD test (Bretz et al 2005)⁴ will be used, with contrasts constructed from the Emax model with candidate ED₅₀ values of 0.5, 1, 3, 7, 15 and 30 mg. Example R function code will be provided in the Programmer's Analysis & Reporting documentation.

5.2.3. Analyses for Categorical Data

Categorical data (eg, CCI and CCI) will show the number and percentage of subjects for each category and include mean/median descriptive statistics similar to the continuous data (See Section 5.2.2). Analysis of the categorical data will use Cochran-Mantel-Haenszel methods, where row-mean-score-difference tests use ridit scores that yield nonparametric analyses. Each PF-06649751 treatment dose will be separately compared to placebo controlling for the geographic region effect.

5.3. Methods to Manage Missing Data

For the analysis of safety endpoints, the sponsor data standard rules for imputation will be applied (eg, partial dates for AEs and concomitant medications will be imputed according to Pfizer standard algorithms).

For the Hauser home diary data, an algorithm is used to handle missing 30-minute intervals (See Section 3.1). A summary of missing diary data will be presented by treatment group.

For scales used in this study, scores will be imputed according to the imputation rules and algorithms for missing component scores that are provided in the data standard documents, or scale documentation. Details are included for each endpoint in Section 3.

Efficacy endpoint analyses in this study will be primarily based on observed cases (OC) and missing data will not be imputed, except for CCI, in which case last observation carried forward (LOCF) will be utilized.

Efficacy and safety analyses will be based on nominal visits as recorded on the CRFs. The only exception will be the early termination (ET) visit if a subject terminates before completion of Week 15. If the subject terminates before Week 15, the data collected at the early termination visit will be assigned to the closest planned visit (target day) for that efficacy or safety assessment. If the early termination visit is equidistant to 2 visits, it will be assigned to the later visit. If the early termination visit is associated with a visit that already exists, the non ET visit will be the representative visit. However, for purposes of LOCF, if more than one value is in a visit window the latter value will be used to carry forward. For all safety categorical determinations, early termination and unplanned visits are considered even if they are not assigned to a visit.

If a subject is missing Baseline (eg, Day 0), the last measurement, taken prior to first exposure to the investigational product, will be used.

Concentrations below the limit of quantification

In all data presentations (except listings), concentrations below the limit of quantification (BLQ) will be set to zero. (In listings BLQ values will be reported as “<LLQ”, where LLQ will be replaced with the value for the lower limit of quantification).

Deviations, missing concentrations and anomalous values

In summary tables and plots of median profiles, statistics will be calculated having set concentrations to missing if 1 of the following cases is true:

1. A concentration has been collected as ND (ie, not done) or NS (ie, no sample);
2. A deviation in sampling time is of sufficient concern or a concentration has been flagged anomalous by the pharmacokineticist.

Note that summary statistics will not be presented at a particular time point if more than 50% of the data are missing.

